# 7.1 Hypothesis

The implant procedure is defined as successful if the responder rate is equal to or greater than 75%. The corresponding statistical hypothesis is therefore as follows:

H 0 (null hypothesis):	$\pi < 0.75$

Ha (alternative hypothesis):  $\pi \ge 0.75$ 

where  $\pi$  is the true proportion of eyes that achieve the performance endpoint (i.e. UCNVA of Snellen equivalent 20/40 or better at 40 cm) at 6 months after implantation (6-month responder rate).

#### 7.2 Study Endpoints

#### 7.2.1 Performance Endpoints

The primary performance endpoint is defined as achievement of monocular UCNVA of Snellen equivalent 20/40 or better at 40 cm at Visit 5 (6 months after implantation) in equal to or greater than 75% of implanted eyes (responder rate).

Fleming's two-stage design was used, which enables early termination of the study at an interim analysis for futility or performance. Here, an interim analysis will be performed with the results obtained from 27 subjects (54 eyes). If there are 43 or less responses, the trial will be stopped for futility since the likelihood of still obtaining a significant result is too low to continue the study under ethical considerations. If there are 48 or more responses observed at the interim analysis, the trial will be stopped and the null hypothesis rejected as enough statistical evidence has been accrued to determine that, within the certainty of the controlled one-sided type I error probability of 2.5%, the true responder rate is greater or equal to 75%.

Otherwise, 16 additional patients (32 eyes) will be recruited for a total of 43 patients (86 eyes). The null hypothesis will be rejected if 73 or more responses are observed among the 86 eyes. This design yields a one-sided type I error probability of 2.5% and a power of 80% if the true response rate is 87.5%.

Secondary performance endpoints include the following:

- Percentage of implanted eyes achieving monocular UCNVA of Snellen equivalent 20/40 or better at 40 cm at Visit 3 and 4 (1 and 3 months after implantation respectively)
- Change from baseline in monocular uncorrected intermediate visual acuity (UCIVA) at 80 cm at postoperative Visit 3, 4 and 5
- Change from baseline in monocular UCNVA at 40 cm at postoperative Visit 3, 4 and 5
- Change from baseline in monocular distance corrected intermediate visual acuity (DCIVA) at 80 cm at postoperative Visit 3, 4 and 5
- Change from baseline in monocular distance corrected near visual acuity (DCNVA) at 40 cm at postoperative Visit 3, 4 and 5
- Change from baseline in binocular UCNVA at 40 cm at postoperative Visit 3, 4 and 5

There are no prespecified performance targets for secondary performance endpoints. 95% confidence limits will be calculated for all secondary performance endpoints.

#### 7.2.2 Safety Endpoint

Ocular AE rates will be assessed for all implanted eyes. There are no prespecified performance targets for the safety endpoint.

# 7.3 Sample Size

Fleming's two-stage design was used to optimize the sample size while allowing for early termination of the trial for futility or performance. It is expected that 90% of eyes will achieve the performance endpoint and the sample size was therefore conservatively determined based on an 87.5% responder rate.

Based on Fleming's two-stage design, 27 subjects (54 eyes) will be enrolled prior to the interim analysis. In case the study is not terminated due to futility or reaching the performance endpoint, an additional 16 subjects (32 eyes) will be enrolled for a total of 43 patients (86 eyes). To allow for 10% attrition over 6 months, a total of 48 subjects (96 eyes) will be enrolled for assessment of the primary and secondary performance endpoints and the primary safety endpoint in case the study is not terminated after the first stage.

This design yields a one-sided type I error probability of 2.5% and a power of 80% if the true response rate is 87.5%.

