Statistical methods:	The primary performance endpoint is defined as achievement of monocular UCNVA of Snellen equivalent 20/40 or better at 40 cm at Visit 5 (6 months after implantation) in equal to or greater than 75% of implanted eyes (responder rate). The analysis will be performed on all	

STAAR Surgical Company Study #CP17-01		
	eyes.	
	The implant procedure is defined as successful if the responder rate is equal to or greater than 75%. The corresponding statistical hypothesis is therefore as follows:	
	H 0 (null hypothesis): $\pi < 0.75$	
	H a (alternative hypothesis): $\pi \ge 0.75$	
	where $\pi$ is the true proportion of eyes that achieve the performance endpoint at 6 months postoperative (6-month responder rate). Fleming's two-stage design was used to optimize the sample size while allowing for early termination due to rejecting the null hypothesis. It is expected that 90% of eyes will achieve the performance endpoint and the sample size was therefore conservatively determined based on an 87.5% responder rate.	
	In the first stage, 27 patients (54 eyes) will be evaluated. If there are 43 or less response the trial will be stopped for futility since the likelihood of still obtaining a significant result is too low to continue the study under ethical considerations. If there are 48 or more responses the trial will be stopped and the null hypothesis rejected as enough statistical evidence has been accrued to determine that, within the certainty of the controlled one-sided type I error probability of 2.5%, the true responder rate is not lower than 75%.	
	Otherwise, 16 additional patients (32 eyes) will be recruited for a total of 43 patients (86 eyes). The null hypothesis will be rejected if 73 or more responses are observed among the 86 eyes. This design yields a one-sided type I error probability of 2.5% and a power of 80% if the true response rate is 87.5%.	
	Summaries for continuous variables will include the number of non- missing observations, mean, standard deviation (SD), median, minimum, and maximum. Summaries for discrete variables will include the tabulation of frequencies and percentages.	

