#### 3.2.3 Subject Discontinuation

A subject may be discontinued (at the discretion of the Investigator, the Sponsor and/or the EC) prior to the final study visit for several reasons, including, but not limited to:

- voluntary withdrawal
- death
- surgical complication preventing implantation of the study lens
- explant of the study lens(es)

If the study lens is explanted, a minimum of one post-explant visit should be completed to record safety measures for the subject (e.g., BCDVA, cataract/lens evaluation, endothelial cell count, etc.).

Prior to discontinuing a subject, every effort should be made to contact the subject, schedule a final study visit, and obtain as much follow-up data as possible.

Adverse events will be followed as described in Section 6.3.5. Subject withdrawals will be documented clearly on the source document and applicable CRF.

Only subjects who do not receive successful bilateral implantation MAY be replaced. Subjects who are discontinued from the study following treatment will not be replaced.

Discontinued subjects should be followed outside of the study protocol according to the Investigator's normal postoperative standard of care.

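### Stage 1 enrols exactly the 27 subjects (54 eyes) the interim needs, with no attrition allowance, no replacement of treated dropouts and no rule for fewer than 54 evaluable eyes

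*Combined protocol and SAP*

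**What the plan says.** - **Stage 1 enrolment.** Section 7.3: "27 subjects (54 eyes) will be enrolled prior to the interim analysis".
- **Stage 1 data needed.** Section 7.2.1: "an interim analysis will be performed with the results obtained from 27 subjects (54 eyes"). The Synopsis: "In the first stage, 27 patients (54 eyes) will be evaluated". The endpoint is read at Visit 5, six months after implantation.
- **Limits.** The Synopsis and sections 7.2.1 and 7.5 give counts: 43 or fewer responses stops for futility, 48 or more rejects the null hypothesis, and otherwise 73 or more of 86 eyes is needed at the end. Section 7.5 ties the interim counts to the 54 eyes. It also says that threshold and observed responder rates are compared, but gives no threshold as a rate.
- **Attrition.** Section 7.3: "To allow for 10% attrition over 6 months, a total of 48 subjects (96 eyes) will be enrolled", in the event that the study continues past the first stage.
- **Replacement.** Section 3.2.3: "Subjects who are discontinued from the study following treatment will not be replaced". Only subjects without successful bilateral implantation may be replaced.
- **Analysis set.** Under section 7.5 the primary analysis uses the Full Analysis Set and the Per Protocol Set. An eye without primary endpoint data is in neither.

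**The concern.** The number enrolled before the interim equals the number of completers the interim needs. The plan expects to lose subjects over six months and budgets for it, but only in the final total. Stage 1 has no margin, treated dropouts cannot be replaced, and further subjects are released only once the interim has been passed. A shortfall below 54 eyes is therefore the usual case under the plan's own assumption.

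What is at stake is a stop/go decision. A limit of 43 is a rate of 79.6% on 54 eyes (43/54) but 89.6% on 48 eyes (43/48), which is above the 87.5% rate the trial is powered to detect. In an open-label, single-arm study, a decision on how to treat a short denominator could be made with the responses already known.

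**Working it through.** **Inputs.** Null rate 75% (section 7.1). Design rate 87.5%, one-sided type I error 2.5%, power 80%, expected rate 90%, 10% attrition, 27 and 43 subjects (section 7.3). Limits 43, 48 and 73 (section 7.2.1). Eyes are treated as independent, as the plan's binomial design implies.

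**1. Reproduce the plan's design.** With X1 ~ Bin(54, p) and X2 ~ Bin(32, p), the probability of success is P(X1 ≥ 48) + Σ over x = 44 to 47 of P(X1 = x) · P(X2 ≥ 73 − x).

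- p = 0.75: 0.0096 + 0.0136 = 0.0232, within the 2.5% limit.
- p = 0.875: 0.4799 + 0.3372 = 0.8171, against 80% stated.
- Futility, P(X1 ≤ 43): 6.8% at 87.5% and 1.7% at 90%.
- Attrition: 43/0.9 = 47.8, rounded up to 48, as stated.

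The stated design holds when 54 eyes are evaluable at the interim.

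**2. Does stage 1 deliver 54 eyes?** Expected completers are 27 × 0.9 = 24.3 subjects, or 48.6 eyes. The chance that all 27 are retained, with independent 10% losses, is 0.9^27 = 5.8%.

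**3. If the fixed counts are applied to the eyes available.** Futility is P(X ≤ 43) and early success is P(X ≥ 48), with X ~ Bin(n, p). Overall power uses the formula in step 1 with n interim eyes and 86 − n further eyes.

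| Evaluable eyes (subjects lost) | Futility at 87.5% | Futility at 90% | Early success at 87.5% | Overall power at 87.5% |
|---|---|---|---|---|
| 54 (0) | 6.8% | 1.7% | 48.0% | 81.7% |
| 52 (1) | 19.6% | 7.1% | 20.5% | 74.1% |
| 50 (2) | 43.6% | 23.0% | 4.2% | 54.5% |
| 48 (3) | 73.3% | 53.1% | 0.2% | 26.5% |

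Averaged over the number retained, K ~ Bin(27, 0.9) with 2K eyes, the futility probability is 59.1% at 87.5% and 45.4% at 90%.

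**4. Sensitivity to pairing of eyes.** The documents give no within-subject correlation. Assuming 0.3 to 0.8, futility at 87.5% is 66% to 70% with 24 subjects, 43% to 44% with 25, and 9% to 13% with all 27. The pattern does not depend on independence.

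**5. Check the remedy.**

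- Stage 1 inflated as the plan inflates the total: 27/0.9 = 30 subjects. P(at least 27 of 30 complete) = P(Bin(30, 0.9) ≥ 27) = 64.7%, so 30 alone does not secure 54 eyes.
- Limits scaled to n eyes, rounding 43n/54 down and 48n/54 up, with the final rule kept at 73 of 86:

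| Evaluable eyes | Stop at or below | Succeed at or above | Futility at 87.5% | Power at 87.5% | Type I error |
|---|---|---|---|---|---|
| 52 | 41 | 47 | 5.4% | 81.5% | 2.1% |
| 50 | 39 | 45 | 4.2% | 82.0% | 2.2% |
| 48 | 38 | 43 | 7.0% | 81.4% | 2.4% |

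**The case against.** The strongest reply is that the plan never tells anyone to apply 43 and 48 to fewer than 54 eyes. Section 7.5 attaches both limits to the 54 eyes, section 7.2.1 speaks of results obtained, and the Synopsis says evaluated. On that reading the interim waits for 54 eyes with data. Section 7.5 also mentions comparing rates, and 43/48 = 89.6% is far above the 79.6% futility rate. Under either reading the wrong-futility risk stays near 7%. The 10% is also a planning allowance, not a forecast. Finally, section 7.0 defers further statistical detail to the SAP, and no separate SAP text is visible in the combined document.

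Much of this stands. A reader might infer that the futility count would stop a lens performing at target. The documents do not support that. The outcome is a probability, it depends on a reading the plan does not adopt, and at the expected 90% rate it is near a coin toss even on that reading. "Target" is also ambiguous, because 75% is the null boundary and 87.5% the design rate. Nor is false success inflated: with fixed counts on 48 eyes the type I error falls to about 0.2%.

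What does not stand is the idea that these readings close the gap. Waiting for 54 evaluable eyes after any loss means implanting more than 27 subjects, which section 7.3 releases only if the study continues past the interim. The ceiling of 48 subjects in section 3.2 does not alter that sequence. A comparison of rates would need stated thresholds and a rounding rule, and section 7.5 gives only counts.

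**Conclusion.** The point holds as a mismatch between stage 1 enrolment and the interim's data requirement. At 10% loss, stage 1 as enrolled yields the 54 eyes behind the limits, and behind the claimed "one-sided type I error probability of 2.5% and a power of 80% if the true response rate is 87.5" percent, only about 6% of the time, and nothing visible says what to do otherwise.

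The size of the harm is conditional. If the fixed counts were used on the eyes available, the futility risk at 87.5% would rise from 6.8% to about 59% averaged over random dropout (44% with two subjects lost, 73% with three), and to about 45% at 90%. Overall power would fall from 81.7% to 54.5% with 50 interim eyes or 26.5% with 48. If the interim waits for 54 eyes or uses rates, the risk stays near 7%. These figures rest on subject-level losses of 10% that are independent and unrelated to response, on independent eyes, and on 86 eyes at the final analysis. The documents do not show that a working lens will be stopped.

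**What to change.** 1. **Section 7.3:** apply the 10% allowance to stage 1 and enrol 30 subjects before the interim, within the existing maximum of 48.
2. **Sections 7.2.1 and 7.5 and the Synopsis:** hold the interim on the first 27 subjects in enrolment order who have Visit 5 UCNVA results in both eyes (54 eyes). State that 43 and 48 apply only to 54 evaluable eyes. Defining the cohort by available results lets subjects 28 to 30 fill gaps.
3. **Fallback:** because 30 enrolled gives at least 27 completers only about 65% of the time, prespecify limits for fewer eyes, to be used once every stage 1 subject has passed the Visit 5 window. The scaled limits above would serve; for example, with 48 eyes stop at 38 or fewer and succeed at 43 or more (power 81.4%, type I error 2.4%, eyes independent).
4. **Section 7.5:** state whether counts or rates decide, and remove the other wording.

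**Cost.** These are wording changes, and maximum enrolment is unchanged. About 3 of the 48 subjects are implanted before the interim rather than after it. One limit remains: if six of the 30 were lost, the remaining 48 − 30 = 18 subjects could bring the total to at most 24 + 18 = 42 subjects (84 eyes). The 86-eye final rule would then also need a stated version for fewer eyes.

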# 3.0 STUDY DESIGN

#### 3.1 Description of Study Design

This is a prospective, open-labeled, multi-site evaluation of clinical performance of the CE-Marked EDOF ICL for the improvement of UCNVA. Approximately 48 subjects who meet all eligibility criteria will undergo phakic IOL implantation in both eyes. All eyes will be followed for 6 months after surgery.

The first eye implanted with the study lens and the appropriate time for fellow eye implantation will be determined by the medical judgement of the Investigator. All eyes will be analyzed for safety and performance.

The subject will have completed the entire study when the study lenses have been implanted bilaterally and the Sponsor receives completed case report form (CRF) documentation for all visits. A Study Exit CRF for each eye must be completed for all subjects enrolled in the study.

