# 3.2 Selection of Study Population

A total of up to 48 subjects (96 eyes) at approximately 6 clinical sites in the EU who meet all eligibility criteria will be offered enrollment into this study.

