# 7.5 Statistical Analysis

#### Primary analysis:

The analysis of the primary performance endpoint is based on Fleming's two-stage design. Threshold responder rates and observed responder rates will be compared to determine if the study is discontinued for futility or achievement of the performance endpoint. The performance endpoint is met and the null hypothesis will be rejected at least 48 responses were observed among the 54 eyes at the interim analysis or 73 responses of 86 eyes at the study end. Conversely, the study will be terminated prematurely for futility if 43 or less responses were observed among the 54 eyes at the interim analysis will be rejected if less than 73 responses were observed at the study end. This analysis yields a power of 80% and a one-sided type I error probability of 2.5% for the targeted sample size.

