#### **Full Analysis Set:**

The FAS contains the data of each eye in the SES for which data has been collected for the primary performance endpoint.

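### If the trial reaches its final stage, the success rule is defined only for 86 evaluable eyes, although up to 96 are enrolled and every eye with endpoint data is analysed

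*Combined protocol and SAP*

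**What the plan says.** The final-stage rule appears in the Synopsis (Statistical methods), Section 7.2.1 and Section 7.5, each time for a single denominator. Section 7.2.1 reads "The null hypothesis will be rejected if 73 or more responses are observed among the 86 eyes".

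Other sections allow a different denominator:

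- Section 7.3 inflates 86 eyes to 96: "To allow for 10% attrition over 6 months, a total of 48 subjects (96 eyes) will be enrolled". Section 3.2 sets the same ceiling: "A total of up to 48 subjects (96 eyes) at approximately 6 clinical sites in the EU".
- Section 3.1: "All eyes will be analyzed for safety and performance". The Full Analysis Set has no cap at 86: "The FAS contains the data of each eye in the SES for which data has been collected for the primary performance endpoint".
- Section 3.2.3 does not replace treated subjects who drop out.
- Section 7.5 runs the primary endpoint on both the Full Analysis Set (FAS) and the Per Protocol Set (PPS). The PPS is a subset of the FAS and so can have its own denominator. Neither set is named as deciding.

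The error claims in Section 7.5 are tied to the planned number: "This analysis yields a power of 80% and a one-sided type I error probability of 2.5% for the targeted sample size". Section 7.0 leaves further detail to a Statistical Analysis Plan, and no separate SAP text is in the document reviewed.

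**The concern.** A count-based cut-off is valid only for the denominator for which it was computed. Here the planned surplus of eyes exists because the number lost is uncertain, yet the rule fits one outcome of that loss. With more than 86 evaluable eyes, keeping 73 loosens the test beyond the stated 2.5%. With fewer, it tightens the test and gives up power for no gain. If the denominator becomes known before anyone has fixed how to handle it, the choice of cut-off could decide whether the trial succeeds. Section 7.5 does not help: its closing words, "will be rejected if less than 73 responses were observed at the study end", give no denominator and sit in a broken sentence.

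**Working it through.** **Inputs.** Null rate 0.75 and planning rate 0.875 (Sections 7.1, 7.3). Interim at 54 eyes, futility at 43 or fewer responses, success at 48 or more, final cut-off 73 of 86 (Section 7.2.1). 48 subjects, 10% attrition (Section 7.3). Eyes are treated as independent. That is an assumption, but it is the one under which the plan's own figures reproduce.

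**Formula.** With X1 ~ Bin(54, p) and X2 ~ Bin(N − 54, p), and final cut-off r:

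P(reject) = P(X1 ≥ 48) + Σ over x = 44..47 of P(X1 = x) · P(X2 ≥ r − x)

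**The plan's own design, N = 86, r = 73.**

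- At p = 0.75: 0.0096 + (0.0726·0.0252 + 0.0484·0.0698 + 0.0284·0.1530 + 0.0145·0.2779) = 0.0096 + 0.0136 = 0.0232.
- At p = 0.875: 0.4799 + 0.3372 = 0.8171.
- A cut-off of 72 gives 0.0362 at p = 0.75, so 73 is the smallest valid count.
- Attrition: 43/0.9 = 47.8, rounded up to 48 subjects; 96 × 0.9 = 86.4 eyes.

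The stated 2.5% and 80% are therefore met at 86 eyes.

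**How often the final cut-off is used.** P(44 ≤ X1 ≤ 47) is 0.164 at p = 0.75, 0.452 at 0.875 and 0.277 at 0.90.

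**How often N is 86, given that stage 2 is reached.** Assume each of 48 subjects is lost with both eyes, independently, with probability 0.10. With K ~ Bin(48, 0.9) and N = 2K: P(N > 86) = 0.469, P(N = 86) = 0.185, P(N < 86) = 0.347.

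**Effect of keeping 73 at other N** (interim included):

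| Final N | Type I error, r = 73 | Power at 0.875, r = 73 | Smallest r with type I error ≤ 0.025 | Its type I error | Its power at 0.875 |
|---|---|---|---|---|---|
| 84 | 0.0127 | 0.6823 | 72 | 0.0179 | 0.7656 |
| 86 | 0.0232 | 0.8171 | 73 | 0.0232 | 0.8171 |
| 88 | 0.0460 | 0.8938 | 75 | 0.0196 | 0.7988 |
| 90 | 0.0790 | 0.9225 | 77 | 0.0168 | 0.7801 |
| 96 | 0.1578 | 0.9319 | 81 | 0.0228 | 0.8480 |

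The 96-eye row is the no-loss extreme. At 84 eyes, part of the drop from 0.8171 is simply fewer eyes. Only the step from 0.6823 to 0.7656 can be recovered by the cut-off.

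**Averaged over the loss distribution,** a fixed 73 has type I error 4.4% at 10% subject loss, 9.8% at 5% and 1.9% at 15%. If single eyes rather than subjects are lost independently at 10%, it is 3.7%.

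**A rate rule** (smallest count that is at least 73/86 of N) has type I error between 0.0148 and 0.0232 for N = 81 to 96.

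**The case against.** The strongest reply is that 96 eyes were chosen so that about 86 remain, and that the rule is right there. Both statements are true, but 86.4 is only an expected value. Under the loss model above, 86 is missed in about 82% of trials that reach stage 2.

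Second, the interim often settles the primary endpoint. At the expected 90% rate, 70.7% of trials succeed at 54 eyes and 1.7% stop for futility. That stands, and it limits how often the gap matters. It does not lower the type I error figures, which already include the interim.

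Third, Section 7.0 defers detail to the SAP, and a denominator rule and a deciding set are usual SAP content. This also stands: the protocol text is silent, but absence from the SAP cannot be shown.

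Three stronger readings are tempting and should not be drawn:

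- A reader might infer that the protocol prescribes 73 at any N, and so a 15.8% error. The clause without a denominator is a fragment of a garbled sentence, and Section 7.5 has just given 73 as a count out of 86. The text is silent at other N; it does not set a fixed count.
- A reader might infer two competing rules, a count and a rate, from "Threshold responder rates and observed responder rates will be compared". That sentence goes on to speak of discontinuing the study, so it fits the interim at least as well, and 73/86 is nowhere called a rate.
- A reader might infer an arithmetic error. There is none: 73 of 86 and the inflation to 48 subjects both check.

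**Conclusion.** The point holds as a gap in the decision rule and should be fixed. The rule is correct at 86 evaluable eyes and undefined elsewhere, and among trials that reach stage 2 the denominator will more often than not be something else. If 73 were carried over unchanged, overall type I error would average 4.4% at the planned 10% attrition when whole subjects are lost, would exceed 2.5% at every N from 87 to 96, and would reach 4.6% at 88 eyes and 7.9% at 90. Below 86 the cost is avoidable loss of power.

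These sizes assume independent eyes, an interim on exactly 54 eyes and loss unrelated to outcome. Fellow-eye correlation is a separate matter. For scale, with an assumed correlation of 0.3 to 0.7, 73 of 86 itself has type I error 4.2% to 7.1%, and a denominator rule does not cure that.

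**What to change.** In the Synopsis and Sections 7.2.1, 7.3 and 7.5, replace the single count with the smallest count for each final N that keeps exact two-stage type I error at or below 2.5% (54-eye interim, bounds 43 and 48):

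| N | 81 | 82 | 83 | 84 | 85 | 86 | 87 | 88 | 89 | 90 | 91 | 92 | 93 | 94 | 95 | 96 |
|---|---|---|---|---|---|---|---|---|---|---|---|---|---|---|---|---|
| Cut-off | 69 | 70 | 71 | 72 | 73 | 73 | 74 | 75 | 76 | 77 | 77 | 78 | 79 | 80 | 80 | 81 |

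Use the same definition for any other N, and recompute if the interim does not have exactly 54 eyes. A one-line rule based on the 73/86 rate is a simpler alternative. It also holds 2.5% for 81 to 96 eyes and gives the same cut-offs except at 91, 92, 95 and 96, where it asks for one more response and costs 5.4 to 6.5 points of power at 87.5%.

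Name one deciding set, FAS or PPS, with the other supportive. Repair the broken sentence in Section 7.5. State that the cut-offs assume independent eyes. If the SAP already contains such a rule, cite it in the protocol instead. Whichever route is taken, settle it before outcome data are seen.

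The cost is wording and a 16-row table; the 48 subjects do not change. The bar rises above 73 when more than 86 eyes are evaluable. Power at 87.5% runs from 75.5% to 85.5% across 81 to 96 eyes, so it is below 80% at some denominators.

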# 7.4 Study Populations

Subjects aged 35-60 that meet the eligibility criteria will be included in the study. No subgroup analysis is planned and subjects will not be stratified into different groups. Furthermore, there are no control groups as the achievement of a VA threshold is assessed for each eye and further analysis aims at assessing the improvement of VA from baseline to follow-up visit for each eye

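### The stated 2.5% one-sided type I error holds only if a subject's two eyes respond independently; with paired eyes the same counts give 2.9% to 7.1% for assumed correlations of 0.1 to 0.7

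*Combined protocol and SAP*

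**What the plan says.** Both eyes of each subject receive the lens, and the eye is the unit of analysis throughout. Section 3.1 says "All eyes will be analyzed for safety and performance". Section 7.4 says that "the achievement of a VA threshold is assessed for each eye". Section 7.1 defines the parameter as a proportion of eyes, with a null boundary of 75%.

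The decision rule is in the Synopsis and in Sections 7.2.1 and 7.5. The Synopsis begins it with "In the first stage, 27 patients (54 eyes) will be evaluated". The trial stops for futility at 43 or fewer responses and stops for success at 48 or more. Otherwise 16 more subjects (32 eyes) are added, and "The null hypothesis will be rejected if 73 or more responses are observed among the 86 eyes".

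The error rate is attached to these counts without condition. Section 7.3 says "This design yields a one-sided type I error probability of 2.5% and a power of 80% if the true response rate is 87.5" (per cent). Section 7.5 says "This analysis yields a power of 80% and a one-sided type I error probability of 2.5% for the targeted sample size". Section 7.2.1 describes a stop for success at the interim analysis as showing that, "within the certainty of the controlled one-sided type I error probability of 2.5%, the true responder rate is greater or equal to 75" (per cent).

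No visible section mentions correlation between fellow eyes, a design effect, a clustered variance or an analysis of one eye per subject. Section 7.0 leaves further statistical detail to the SAP.

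**The concern.** A count of 54 eyes from 27 people carries the information of 54 independent observations only if one eye's result says nothing about the other's. If fellow eyes tend to succeed or fail together, the number of responders varies more than a binomial count does. The variance of a subject's total is 2p(1−p)(1+ρ), where ρ is the fellow-eye correlation, instead of 2p(1−p). A fixed high threshold is then crossed by chance more often.

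The documents give reasons to expect a positive ρ. Age (35 to 60, Section 7.4) is the same for both eyes, and the degree of presbyopia, reflected in the required reading add of +1.00 to +2.50 D (Section 3.2.1.1), is largely shared. Other features pull ρ down. The eligibility limits narrow the differences between subjects, and refractive factors can differ between eyes; Appendix B, for instance, allows ±0.50 D of latitude in the refractive target.

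The trial's one confirmatory claim is at stake, together with the option to stop early and declare success. Both rest on the 2.5%.

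**Working it through.** **Inputs from the protocol.** Null boundary p = 0.75 (Section 7.1). Design alternative p = 0.875 (Section 7.3). Stage 1: 27 subjects, 54 eyes, futility at ≤43, success at ≥48. Stage 2: 16 more subjects, 32 eyes, success at ≥73 of 86 (Section 7.2.1).

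**Assumed input.** Fellow-eye correlation ρ. The documents give none, so a range is shown.

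**Step 1: reproduce the stated figures with independent eyes.**

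P(reject) = P(X₁ ≥ 48) + Σ P(X₁ = x)·P(X₂ ≥ 73 − x), summed over x = 44 to 47, with X₁ ~ Bin(54, p) and X₂ ~ Bin(32, p).

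- At p = 0.75: 0.0096 + 0.0136 = 0.0232.
- At p = 0.875: 0.8171.
- Lowering either success count by one breaks the limit: 47 with 73 gives 3.36%, and 48 with 72 gives 3.62%.

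The counts therefore fit an independent-eye design held to 2.5% and 80%. The protocol does not state independence; it is inferred from this match and from the silence on pairing.

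**Step 2: the same counts with paired eyes.** With q = 1 − p, each subject contributes

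- 2 responses with probability p² + ρpq,
- 1 response with probability 2pq(1 − ρ),
- 0 responses with probability q² + ρpq.

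For example, at p = 0.75 and ρ = 0.3, pq = 0.1875 and ρpq = 0.05625. The three probabilities are 0.61875, 0.2625 and 0.11875. Convolving over 27 and then 16 subjects and applying the unchanged rule gives:

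| ρ (assumed) | Type I error at 75% | Power at 87.5% | True rate at which rejection probability is exactly 2.5% |
|---|---|---|---|
| 0 | 2.3% | 81.7% | 75.2% |
| 0.1 | 2.9% | 80.7% | 74.6% |
| 0.3 | 4.2% | 79.0% | 73.6% |
| 0.5 | 5.6% | 77.5% | 72.6% |
| 0.7 | 7.1% | 76.3% | 71.6% |

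The type I error passes 2.5% just above ρ = 0.03. A beta-binomial simulation of 400,000 trials agrees: 2.90% at ρ = 0.1 and 7.16% at ρ = 0.7.

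**Step 3: incomplete pairs.** Some subjects may contribute only one eye, because "The FAS contains the data of each eye in the SES for which data has been collected for the primary performance endpoint". Suppose 4 single-eye subjects per stage (assumed: 25 pairs + 4, then 14 pairs + 4, so still 54 and 32 eyes). The type I error is then 2.9%, 4.1%, 5.3% and 6.7% at ρ = 0.1, 0.3, 0.5 and 0.7.

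**The case against.** The strongest reply concerns size. No ρ is given, and at 0.1 the excess over 2.5% is only 0.4 points. At ρ of 0.3 to 0.5 the counts still control 2.5% against a true rate of 73.6% to 72.6%, a shift of 1.4 to 2.4 points from 75%. At the 90% rate the sponsor expects, the rule still succeeds with probability 92.8% (ρ = 0.3) or 91.3% (ρ = 0.5). This is also a single-arm, open-label study of a CE-marked lens, and the SAP may contain a clustered analysis. All of that is fair. It means the error matters mainly when the true rate is near 75%, and that the amount of inflation is conditional.

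It does not restore the stated figure. The protocol gives 2.5% without condition, offers no argument for a correlation near zero, and ties the number to fixed counts. An additional SAP analysis could not make that statement true, and a different SAP rule would conflict with the protocol.

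Two narrower points stand. The result for incomplete pairs applies to few single eyes. With 14 and 12 single eyes (20 and 10 pairs, also assumed), the type I error at ρ = 0.5 is 4.6% instead of 5.6%. The power claim is also affected: power falls below 80% by ρ = 0.2 (79.8%).

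**Conclusion.** The concern holds. The stated 2.5% is correct for these counts only when fellow-eye correlation is about 0.03 or less. The direction for any larger positive correlation is certain. The size depends on a correlation the documents do not supply: a modest excess at 0.1, and more than double the stated level at 0.5. Power falls more slowly. The headline range assumes complete pairs in both stages and the boundaries as written. Because an unconditional error rate appears in four places and supports both the final claim and the early success stop, it should be corrected before the interim analysis. A later change of boundary or error rate could look driven by the data.

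**What to change.** In the Synopsis and Sections 7.2.1, 7.3 and 7.5, say that 2.5% and 80% assume independent eyes, and tabulate type I error and power over a range of ρ that the sponsor justifies. Then choose one route before the interim analysis.

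**Route 1: keep the counts and restate the error rate.** Suggested text: *Boundaries were derived for independent eyes (exact one-sided type I error 2.3%, power 81.7% at 87.5%). With two eyes per subject and fellow-eye correlation of 0.1 to 0.5, exact type I error is 2.9% to 5.6% and power 80.7% to 77.5%.* The cost is wording in four places and one table. Counts and sample size stay the same, but the sponsor must accept a stated type I error above 2.5%.

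**Route 2: keep 2.5% and reset the boundaries** by exact calculation on subjects contributing 0, 1 or 2 responses, up to a pre-specified maximum ρ, which is the sponsor's judgement. Examples with 43 fully paired subjects and futility unchanged:

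| Success counts | Holds 2.5% up to ρ | Power at 87.5% | Power at 90% |
|---|---|---|---|
| ≥49/54 or ≥74/86 | 0.33 | about 71% (ρ = 0.3) | about 89% (ρ = 0.3) |
| ≥49/54 or ≥75/86 | 0.52 | about 63% (ρ = 0.5) | about 82% (ρ = 0.5) |

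The cost is the same wording, new boundaries and the lower power shown. Keeping both 2.5% and 80% at 87.5% would need more subjects than 43; that number is not worked out here.

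These boundaries apply only to 54 and 86 fully paired evaluable eyes. Section 7.3 enrols up to 96 eyes, and the Full Analysis Set keeps only eyes with endpoint data. The SAP should therefore say that the boundaries will be recomputed by the same method for the actual numbers of pairs and single eyes.
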